### **15 RISK ANALYSIS**

#### **15.1 Anticipated Clinical Benefits**

While there are no guaranteed clinical benefits associated with participation in this clinical study, it is expected that patients implanted with a Navitor valve with the FlexNav delivery system will experience similar improvements in symptoms related to severe aortic stenosis as patients implanted with other

## Clinical Investigation Plan

commercially available transcatheter valves. This includes improvements in chest pain, fatigue, shortness of breath, dizziness and fainting.

Although the Navitor Valve and FlexNav Delivery System is not anticipated to add new clinical benefits, the design modifications to the Navitor valve may result in reduced risk for paravalvular leak, minimize vessel trauma, and improved valve expansion, stability and sealing as compared to the first-generation Portico valve.

Similarly, the design features of the FlexNav Delivery System are intended to improve deliverability and deployment accuracy and enhance overall ease of use. Additionally, the Navitor Loading system is designed to accommodate the newly scaled stent aortic heights of the Navitor Valve and a new stent guard component is added to accommodate the atraumatic aortic cells.

### 15.2 Foreseeable Adverse Events and Anticipated Adverse Device Effects

Risks associated with the specified device and procedure, together with their likely incidence, are described in Appendix XV. There may be risks related to the devices under investigation that are unknown at present. Likewise, the exact frequency of the risk may be unknown.

#### 15.2.1 Potential Anticipated Adverse Events

The Navitor TAVI System is not intended or anticipated to introduce any new risks beyond that observed for the current (first-generation) Portico system. For that reason, the potential anticipated adverse events associated with use of the Navitor TAVI System are similar to those associated with any routine TAVR procedure and related follow-up.

As outlined in the IFU, potential anticipated adverse events associated with the use of transcatheter bioprosthetic heart valves include but are not limited to, the following:

- access site complications (e.g., pain, bleeding, infection, hematoma, pseudoaneurysm, etc.)
- acute coronary obstruction
- acute myocardial infarction
- allergic reaction to antiplatelet agents, contrast medium, or valve components
- aortic rupture
- ascending aorta trauma
- atrio-ventricular node block
- cardiac arrhythmias
- conduction system injury
- dissection
- embolism
- endocarditis
- heart failure
- hemodynamic compromise
- hemolysis
- hemolytic anemia
- hemorrhage (bleeding)
- hypotension or hypertension
- infection
- myocardial ischemia
- mitral valve insufficiency

## Clinical Investigation Plan

- multi-organ failure
- non-structural dysfunction (i.e., entrapment by pannus, paravalvular leak, inappropriate sizing or positioning)
- pericardial effusion
- perforation of the myocardium, ventricle, or a blood vessel
- pannus
- regurgitation
- renal insufficiency or renal failure (acute kidney injury)
- respiratory failure
- sepsis
- stroke
- structural deterioration (i.e., calcification, leaflet tear)
- thrombosis
- tamponade
- valve embolization or migration
- vessel dissection or spasm.

It is possible these complications could lead to:

- transfusion
- conversion to open surgical procedure
- reoperation
- emergent balloon valvuloplasty
- emergent percutaneous coronary intervention (PCI)
- emergent surgery (i.e., coronary artery bypass, heart valve replacement)
- explantation
- permanent disability
- death
- permanent pacemaker

Subjects experiencing an adverse event shall be treated per the standard of care at the investigational site.

### 15.3 Residual Risks Associated with the Device Under Investigation, as Identified in the Risk Analysis Report

Risk analysis for the Navitor Transcatheter Aortic Heart Valve, FlexNav Delivery System, and Navitor Loading System will be performed in accordance with the Risk Analysis Plan (internal ref: 90163677). The risk analysis utilizes Hazard Analysis (internal ref: 90163681) and Failure Mode Effect Analysis (FMEA) tools to systematically identify potential hazards associated with the design (internal refs: 90336360, 90163680) and use (internal ref: 90078354) of the devices. All potential harms and hazards associated with Navitor Valve and the FlexNav Delivery System were identified and documented in risk management report. All risks will be reduced as far as possible. Information of residual risks and safety will be provided in the Instruction for Use.

## Clinical Investigation Plan

### 15.4 Risks Associated with Participation in this Clinical Study

Protocol-required assessments are summarized in Table 5. Possible risks and discomforts associated with participation in the study will be similar to those associated with any routine transcatheter aortic valve implantation procedure and related follow-up procedures.

Study-specific assessments that are not considered standard of care include the six-minute walk test, blood collection for laboratory tests, and echocardiogram exam during scheduled follow-up visits (excluding at discharge). Risk associated with blood collection is similar to any routine blood collection and is minimal (e.g., temporary pain and small risk of infection, bleeding, or bruising/swelling at the puncture site), which are mitigate by appropriate cleansing and adherence to standard blood collection procedures. There are no know clinical risks associated with echocardiogram; however a subject may experience mild discomfort from the pressure of the transducer during the exam. A subject may experience fatigue, shortness of breath, chest pain and/or leg cramps during six minute walk test; this is mitigated by performing this test under the supervision of a trained professional and in a testing area where medical care is immediately available.

### 15.5 Steps Taken to Control or Mitigate Risks

In-depth recommendations, special precautions and instructions regarding patient anatomical evaluation, vessel sizing, pre-implantation, implantation and post-implantation precautions are included in the IFU. Furthermore, the IFU also states that the devices can only be used by physicians who have received appropriate training on how to use the device. This statement is interpreted to mean that the physician users are expected to be aware of the known and foreseeable safety risks associated with the use of the devices including the surgical and/or non-surgical treatment of these conditions.

Risks associated with the use of the device under investigation are minimized through device design, investigator selection and training, pre-specified patient eligibility requirements, study monitoring by the sponsor to ensure adherence to the protocol as well as to assess ongoing patient safety.

**Device Design:** Specific features of the device design that to minimize potential risk to subjects are described below.

#### Navitor Valve:

The Navitor transcatheter heart valve is a pericardial tri-leaflet valve in a self-expanding stent designed for intra-annular placement using minimally invasive techniques.

The Navitor Valve maintains several design features of the first-generation Portico Valve including: same valve sizes and use range, open stent cell design to provide easy coronary access and blood flow, repositionable with full ability to re-sheath and retrieve, leaflets derived from pericardial bovine tissue, and low placement of leaflets/cuff within the stent frame for early valve function to maintain hemodynamic stability during implant.

The Navitor Valve incorporates the following key design enhancements to improve upon the first-generation Portico™ valve:

- Addition of a fabric outer cuff to the exterior portion of the stent to optimize valve sealing and improve paravalvular leak performance.

## Clinical Investigation Plan

- Replacement of the inner porcine tissue cuff with the same fabric used for the new exterior cuff to maintain delivery system profile.
- Addition of a slight inward curvature to the aortic end of the stent to minimize vessel trauma and aid retainer release from the FlexNav™ Delivery System
- Adjusted scaling of the stent across all valve sizes to normalize the aortic/annular to stent height ratio.
- Minor stent modifications to the 23 mm and 25mm Navitor Valves to deliver uniform minimum stent/valve chronic outward radial (COR) force across the Portico family to improve valve expansion, stability and sealing.

Similarly, the Navitor Titan Valve maintains those same design features of the first-generation Portico valve and includes the outer fabric cuff and slight inward curvature of the aortic end of the stent. The Navitor Titan valve is designed to provide comparable COR forces as the other Navitor sizes in patients with larger annulus diameters (27-30mm).

### FlexNav Delivery System:

The Navitor valve is loaded onto the FlexNav™ Delivery System which has an equivalent integrated sheath diameter of 14 French for 23 and 25 mm valves and 15 French for 27 and 29 mm valves. The FlexNav Delivery System offers several key features to mitigate risks to patients:

- The delivery system features an integrated sheath with hydrophilic coating on the exterior, which serves as an introducer sheath to decrease the insertion profile into the vasculature.
- Added stability layer on outer membrane shaft acts as a stabilizing layer during deployment by isolating motion between the introducer/vasculature and delivery system to minimize the number of manipulations required during valve deployment
- Stainless steel multifilar shaft increases delivery system tensile strength and flexibility to aid in valve alignment and improve re-sheath closure
- Proximal end of nose cone tip has been modified to be more tapered to minimize potential dislodging of the valve during removal of the delivery system.
- Nose cone profile has been lengthened to facilitate sheathless introduction.
- Handle features an automatically engaged partial deployment release button to retract the outer sheath, releasing the valve.
- The delivery system deploys the valve annulus first to allow gradual deployment of the annular cells. A partially deployed valve's position can be evaluated, and the valve can be re-sheathed and re-deployed (if needed) provided the valve has not been released past the aortic cells. Complete re-sheathing of the partially deployed valve at the implant site is possible by reversing the deployment mechanism.

### Navitor Loading System:

The Navitor Loading System facilitates valve preparation/loading onto the FlexNav Delivery System; the small Navitor loading system is used for loading the 23 or 25mm valves on the small delivery system (14 F equivalent integrated sheath), and the large Navitor loading system is used for loading the 27 or 29mm

## Clinical Investigation Plan

valves on the large delivery system (15 F equivalent integrated sheath). The Navitor Loading System – LG+ is used for loading the Navitor Titan valve on the large delivery system.

- The loading base has been modified to include an integrated guide tube to eliminate the potential for the tip of the delivery system to interact with valve leaflets during loading of the valve onto the delivery system.
- The loading base insert has been modified to fit the new integrated guide tube

**Investigator Selection and Training:** The following risk control measures will be implemented at the investigational site level to minimize potential clinical risks to subjects participating in this clinical study:

- Investigators will be carefully selected based on their knowledge of, and experience implanting and managing, TAVR devices, including Portico TAVI system.
- Interventional cardiologists and cardiovascular surgeons performing procedures must be board certified and experienced with TAVR implantation procedures.
- The local Heart Team's interventional cardiologist(s) and cardiac surgeon(s) jointly participate in the intra-operative technical aspects of TAVR (required for US sites per Medicare NCD).
- Investigators will be extensively trained with regards to implantation technique of the Navitor Valve using the FlexNav Delivery System.
- Investigators will be provided with a Clinical Instructions for Use (IFU) as a reference.
- Procedure setting to include either a hybrid catheterization/operating room suite and/or a fixed C-arm angiography imaging capability in the operative suite for quality imaging.

**Adherence to the Clinical Investigational Protocol:** The clinical study will be monitored by the Sponsor to ensure adherence to the CIP. Subjects will be carefully selected through rigorous screening by both the site's heart team and independent SSC using pre-specified inclusion and exclusion criteria as stated in section 5.3. Additionally, as stated in section 10.9.2, an independent DMC will monitor cumulative data at prescribed intervals and may consider a recommendation for modifications or termination of the study based on any safety concerns. Adverse events and device deficiencies will be reported to Abbott and will be monitored internally for safety surveillance purposes and reported to regulatory authorities as applicable.

### 15.6 Risk to Benefit Rationale

Current medical management guidelines have established TAVR as first-line treatment (Class I indication) for symptomatic severe aortic stenosis in patients considered to be high or extreme risk for surgical aortic valve replacement. Risks associated with the Portico family of valves are the same as other transcatheter heart valves. The anticipated risks are stated in Section 15.2 Foreseeable Adverse Events and Anticipated Adverse Device Effects.

Protocol-required clinical assessments are primarily standard of care assessments for cardiac/structural heart interventional procedures and will be administered per Hospital guidelines. Risks to the subject undergoing study-specific assessments (not considered standard of care) have been addressed in the clinical investigational protocol with appropriate mitigation for each risk to the lowest level possible.

The benefits of the Navitor valve are anticipated to be similar to other transcatheter aortic valves, which may include improvements in chest pain, fatigue, shortness of breath, dizziness and fainting. Clinical evaluation of the Portico valve and first-generation Portico Delivery System in the Portico TAVI System CE

## Clinical Investigation Plan

Mark study and Portico I study support the safety and performance of these devices. While the clinical benefit of the Navitor valve used with the FlexNav delivery system has not been established, the design modifications are not intended to or anticipated to introduce new risks. Collectively, the prior clinical experience with the Portico TAVI system and bench data support that the benefits outweigh the risks associated with the evaluation of this device in a clinical study.

## Clinical Investigation Plan

### 16 APPENDICES

#### APPENDIX I: ABBREVIATIONS AND ACRONYMS

Abbreviation	Term
6MWT	Six Minute Walk Test
ACT	Activated Clotting Time
ADE	Adverse Device Effect
AE	Adverse Event
AF	Atrial Fibrillation
AHA	American Heart Association
AS	Aortic Stenosis
AVA	Aortic Valve Area
AVR	Aortic Valve Replacement
BARC	Bleeding Academic Research Consortium
BNP	B-type Natriuretic Peptide
CAD	Coronary Artery Disease
CBC	Complete Blood Count
CE	Conformité Européene (European Conformity)
CEC	Clinical Events Committee
CIP	Clinical Investigation Plan
CPB	Cardiopulmonary Bypass
eCRF	Electronic Case Report Form
CT	Computed Tomography
CVA	Cerebral Vascular Accident
EC	Ethics Committee
ECG	Electrocardiogram
Echo	Echocardiography
EDC	Electronic Data Capture
EEA	European Economic Area
EF	Ejection Fraction
EOA	Effective Orifice Area
EU	European Union
GI	Gastro Intestinal
HOCM	Hypertrophic cardiomyopathy with or without obstruction
ICF	Informed Consent Form
IDE	Investigational Device Exemption
IFU	Instructions For Use
INR	International Normalized Ratio
KCCQ	Kansas City Cardiomyopathy Questionnaire
Kg	Kilogram
LBBB	Left Bundle Branch Block
LV	Left Ventricular
LVEF	Left Ventricular Ejection Fraction
LVOT	Left Ventricular Outflow Tract
MAC	Mitral Annular Calcification
MI	Myocardial Infarction

## Clinical Investigation Plan

MMSE	Mini-mental state examination
MR	Mitral Regurgitation
MRI	Magnetic Resonance Imaging
mRS	Modified Rankin Scale
NIHSS	NIH Stroke Scale
NYHA	New York Heart Association
PA	Pulmonary Artery
PCI	Percutaneous Coronary Intervention
PCWP	Pulmonary Capillary Wedge Pressure
PI	Principal Investigator
QoL	Quality of Life
PVD	Peripheral Vascular Disease
PVL	Paravalvular Leak
RA	Right Atrium
RV	Right Ventricular
SADE	Serious Adverse Device Effect
SAE	Serious Adverse Event
SAVR	Surgical Aortic Valve Replacement
SSC	Subject Selection Committee
STS	Society of Thoracic Surgeons
TAVI	Transcatheter Aortic Valve Implantation
TAVR	Transcatheter Aortic Valve Replacement
TEE	Transesophageal Echocardiogram (same as TOE)
TIA	Transient Ischemia Attack
TTE	Transthoracic Echocardiogram
UADE	Unanticipated Adverse Device Effect
USA	United States of America (same as US)
VARC 2	Valve Academic Research Consortium 2
WBC	White Blood Cell

## Clinical Investigation Plan

### APPENDIX II: STUDY ENDPOINT DEFINITIONS

Source	Definition
Cardiovascular Mortality (VARC 2)	
Any one of the following criteria:
 
 
• Death due to proximate cardiac cause (e.g. myocardial infarction, cardiac tamponade, worsening heart failure)
 
• Death caused by non-coronary vascular conditions such as neurological events, pulmonary embolism, ruptured aortic aneurysm, dissecting aneurysm, or other vascular disease
 
• All procedure-related deaths, including those related to a complication of the procedure or treatment for a complication of the procedure
 
• All valve-related deaths including structural or nonstructural valve dysfunction or other valve-related adverse events
 
• Sudden or unwitnessed death
 
• Death of unknown cause
 

Myocardial Infarction (VARC 2)	
Peri-procedural MI (less than or equal to (≤) 72 hr after the index procedure)            New ischemic symptoms (e.g., chest pain or shortness of breath), or new ischemic signs (e.g. ventricular arrhythmias, new or worsening heart failure, new ST-segment changes, hemodynamic instability, or imaging evidence of new loss of viable myocardium or new wall motion abnormality),
 
AND
 
Elevated cardiac biomarkers within 72 h after the index procedure consisting of at least one sample post-procedure with a peak value exceeding 15x upper reference limit (troponin) or 5x for CK-MB. If cardiac biomarkers are increased at baseline (>99th percentile), a further increase of at least 50% post-procedure is required AND the peak value must exceed the previously stated limit.
 
Spontaneous MI (greater than (>) 72 hr after the index procedure)            Any one of the following criteria:
 
 
• Detection of rise and/or fall of cardiac biomarkers (preferably troponin) with at least one value above the 99th percentile URL, together with evidence of myocardial ischemia with at least one of the following:               
 
○ Symptoms of ischemia
 
○ ECG changes indicative of new ischemia [new ST-T changes or new Left Bundle Branch Block (LBBB)]
 
○ New pathological Q waves in at least two contiguous leads
 
○ Imaging evidence of new loss of viable myocardium or new wall motion abnormality
 
 
 
• Sudden, unexpected cardiac death, involving cardiac arrest, often with symptoms suggestive of myocardial ischemia, and accompanied by presumably new ST-segment elevation, or new LBBB, and/or evidence of fresh thrombus by coronary angiography and/or at autopsy, but death occurring before blood samples could be obtained, or at a time before the appearance of cardiac biomarkers in the blood.
 
• Pathological findings of an acute myocardial infarction.
 

Stroke (FDA/VARC 2)	
This study is following the FDA's definition of Stroke per FDA's Current Thinking Regarding Neurological Assessments for Transcatheter Valve Trials (Revised: 25 Aug 2011) and VARC 2 (2012)
 
1. Definitions:
 
a. Stroke: Stroke is an acute episode of focal or global neurological dysfunction caused by the brain, spinal cord, or retinal vascular injury as a result of hemorrhage or infarction.
 
Sub classifications of stroke:
 
i. Ischemic Stroke is defined as an acute symptomatic episode of focal cerebral, spinal, or retinal dysfunction caused by an infarction of central nervous system tissue.

## Clinical Investigation Plan

- ii. Hemorrhagic Stroke is defined as an acute symptomatic episode of focal or global cerebral or spinal dysfunction caused by a nontraumatic intraparenchymal, intraventricular, or subarachnoid hemorrhage.
- Stroke Disability (consistent with VARC 2 Definitions):
- i. Disabling: an mRS score of 2 or more at 90 days and an increase of at least one mRS category from an individual's pre-stroke baseline
  - ii. Non-disabling: an mRS score of < 2 at 90 days or one that does not result in an increase of at least one mRS category from an individual's pre-stroke baseline
- b. Cerebral Infarction: Evidence of brain cell death from imaging studies or pathological examination. If there are clinical symptoms, then it is a stroke; otherwise, it is an asymptomatic cerebral infarction.
- c. Transient Ischemic Attack (TIA): A transient (less than (<) 24 hrs) episode of neurological dysfunction caused by focal brain, spinal cord, or retinal ischemia, without acute infarction. No evidence of infarction if imaging performed.
- d. Encephalopathy: Altered mental state (e.g., seizures, delirium, confusion, hallucinations, dementia, coma, psychiatric episode, etc.).
- e. Intracranial Hemorrhage: Collection of blood between the brain and skull. Subcategorized as epidural, subdural, and subarachnoid bleeds.

**Bleeding (VARC 2)**

**Life-threatening or disabling bleeding**

- Fatal bleeding (BARC type 5) **OR**
- Bleeding in a critical organ, such as intracranial, intraspinal, intraocular, or pericardial necessitating pericardiocentesis, or intramuscular with compartment syndrome (BARC type 3b and 3c) **OR**
- Bleeding causing hypovolemic shock or severe hypotension requiring vasopressors or surgery (BARC type 3b) **OR**
- Overt source of bleeding with drop in hemoglobin of greater than or equal to ( $\geq$ ) 5 g/dl or whole blood or packed red blood cells (RBCs) transfusion greater than or equal to ( $\geq$ ) 4 U (BARC type 3b). *Given 1 U of packed RBC typically will raise blood hemoglobin concentration by 1 g/dl, an estimated decrease in hemoglobin will be calculated.*

**Major bleeding (BARC type 3a)**

- Overt bleeding either associated with a drop in the hemoglobin level of at least 3.0 g/dl or requiring transfusion of two or three units of whole blood/ RBC, or causing hospitalization or permanent injury, or requiring surgery **AND**
- Does not meet criteria of life-threatening or disabling bleeding

**Minor bleeding (BARC type 2 or 3a, depending on the severity)**

- Any bleeding worthy of clinical mention (e.g., access site hematoma) that does not qualify as life-threatening, disabling or major

**Acute Kidney Injury (AKIN Classification) (VARC 2)**

Change in serum creatinine (up to 48 hr) compared with baseline

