### 4.3 Descriptive Endpoints

The following key outcomes (relevant to characterizing the safety profile and outcomes based on the design modifications) will be assessed as descriptive endpoints for the study (for both the Portico NG and Titan cohorts, but analyzed independently for each cohort):

- Technical device success defined as successful vascular access, delivery and deployment of the Navitor Valve; retrieval with the delivery system and correct positioning of a single valve in the proper anatomical location and the absence of procedural mortality
- All-cause mortality at 12 months from the index procedure
- Cardiovascular-related mortality at 30 days and 12 months from the index procedure
- Disabling stroke at 30 days and 12 months from the index procedure
- Life threatening and major bleeding at 30 days from the index procedure
- Acute kidney injury at 30 days from the index procedure
- Major and minor vascular complications at 30 days from the index procedure
- Permanent pacemaker insertion at 30 days and 12 months from the index procedure
- Changes in functional status from baseline to follow-up assessments at 30 days and 12 months (e.g., NYHA classification, six-minute walk test, quality of life measures)
- Paravalvular leak at discharge, 30 days and 12 months from the index procedure
- Changes in echocardiographic parameters from baseline to follow-up at 30 days and 12 months (e.g., mean effective orifice area, mean transvalvular gradient, mean peak velocity)
- Symptomatic valve thrombosis at 30 days and 12 months from the index procedure

Additional outcomes to be collected and assessed during the study:

- Myocardial infarction at 30 days and 12 months from the index procedure
- New-onset atrial fibrillation at 30 days and 12 months from the index procedure
- Coronary obstruction requiring intervention at 30 days from the index procedure
- Valve embolization during procedure, and at 30 days and 12 months from the index procedure
- Reintervention to treat valve-related dysfunction at 30 days and 12 months from the index procedure
- Total aortic valve regurgitation (transvalvular plus paravalvular leak) at discharge, 30 days and 12 months from the index procedure

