### 6.1.3 Pre-procedure Blood Tests

The following blood tests will be performed at the investigational site within 72 hours prior to the index procedure:

1. Cardiac enzymes (Troponin or CK/CK-MB)
2. BUN and Creatinine

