## 6.3 Post-procedure (In-hospital)

### 6.3.1 Post-procedure Laboratory Tests

The following laboratory tests should be performed in-hospital post-implant procedure:

1. Troponin, or CK / CK-MB should be collected between approximately 12 and 24 hours after procedure, between approximately 36 and 48 hours after the procedure, and at approximately 72 hours after the procedure (or at discharge, if patient is discharged prior to 72 hours post procedure).
2. BUN and Creatinine to be collected within 72 hours after index procedure

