## 6.4 Discharge Assessments

The discharge visit will take place at the time of hospital discharge or at 7 days after the procedure, whichever occurs first. If the subject is expected to be discharged over the weekend, the discharge tests may be completed on the last week day prior to discharge.

The discharge assessment will include:

1. Physical exam (weight, heart rate, blood pressure)
2. Modified Rankin Scale (mRS)
3. NIH Stroke Scale (NIHSS)

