## Clinical Investigation Plan

4. Barthel Index
5. Echocardiogram (if not performed during the post procedure testing within 48 hours after procedure)
6. 12 lead ECG (for subjects receiving a new permanent pacemaker, ECG should be completed showing the underlying rhythm as well as the current pacing programming)
7. Cardiovascular medications documentation
8. Adverse events assessment
9. Lab Measurements (CBC and Platelet count, BUN and Creatinine, and Troponin or CK/CK-MB if patient is discharged prior to 72 hours post-procedure)

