## Clinical Investigation Plan

Study Activity	Screening	Baseline	Procedure	Discharge	30 days [+21 days]	12 months  [-30/+45 days]	Annual visits (2 through 5 years) [±60 days]
	recommended after adverse events of ischemic stroke and myocardial infarction.						
CT Scan with Angiography for chest, abdomen and pelvis	X (within 12 months of consent)						
Chest X-Ray		X					
Quality of Life Measures							
SF-36		X			X	X	
Lab Measurements							
CBC and Platelet count	X			X	X	X	
BUN and Creatinine	X		X 	X	X	X	
BNP or ProBNP	X				X	X	
INR (if subject is on Coumadin or Warfarin  )		X			X	X	
Troponin or CK / CK-MB		X	X 	(X)	X	X	
Albumin (for Frailty Index)	X				X	X	
Other							
Adverse Event Assessment	X	X	X	X	X	X	X
Deviation	(X)	(X)	(X)	(X)	(X)	(X)	(X)
Device Deficiency			(X)	(X)	(X)	(X)	(X)
Withdrawal			(X)	(X)	(X)	(X)	(X)
Death	(X)	(X)	(X)	(X)	(X)	(X)	(X)

 In the event a 12 month visit per the requirements in the clinical investigational plan is not completed, the site may call the subject to document survival.

 For subjects receiving a new permanent pacemaker, ECG should be completed showing the underlying rhythm as well as the current pacing programming.

 Copy of echocardiographic exam to be stored at the site and available to the Sponsor upon request.

 To be done within 24-48 hours after procedure, or as close to discharge as possible (but no more than 7 days after procedure).

 If CT is contraindicated and/or not possible to be obtained for certain subjects, a 3D TEE and non-contrast CT of chest and abdomen/pelvis may be accepted if approved by the subject selection committee.

 To be collected within 72 hours **before** index procedure and within 72 hours **after** index procedure

 To be collected within 72 hours **before** index procedure and approximately 12-24 hours **after** the procedure, approximately 36-48 hours after the procedure, and at approximately 72 hours (or at discharge, if patient is discharged prior to 72 hours post procedure) to be consistent with VARC II guidelines.

 Subjects may take other anticoagulants/vitamin K antagonists in lieu of warfarin

 Only required if an in-person office visit is conducted

 Required at all annual follow-up visits except for the 3-year visit

(X) indicates if applicable

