### 8.2.5 Secondary Endpoint Analysis

The secondary endpoint is a non-hierarchical composite of all-cause mortality, disabling stroke, life threatening bleeding, acute kidney injury (stage 3), or major vascular complications at 30 days. This endpoint will be analyzed for both the Portico NG and Titan cohorts separately.

The proportion of subjects experiencing a secondary endpoint will be estimated from the binomial model. The 95% confidence intervals will be calculated using the exact Clopper–Pearson method. The estimated secondary endpoint rate at 30 days will be descriptively compared with rates observed with FDA approved TAVR devices studied in the same patient population (e.g., high and extreme risk), including the observed rates and 95% confidence intervals from published sources shown in Table 8 below and data from FDA approved devices available at the time of PMA submission.

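### Creatinine-based AKI is defined over 48 hours, but no post-procedure creatinine is required by 48 hours, so a compliant subject may have no value that can be staged

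*Protocol*

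**What the plan says.** **Definition.** Protocol Appendix II stages AKI on "Change in serum creatinine (up to 48 hr) compared with baseline". Each of the three stages also has a urine-output criterion, and renal replacement therapy counts as stage 3 whatever else is recorded. The start of the 48 hours is not given, nor is the creatinine value that serves as baseline.

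**Sampling.**
- Before the procedure, Section 5.2.1 has a screening creatinine. Section 6.1.3 adds BUN and creatinine: "The following blood tests will be performed at the investigational site within 72 hours prior to the index procedure".
- After the procedure, Section 6.3.1 has "BUN and Creatinine to be collected within 72 hours after index procedure". Footnote 6 of Table 5 says the same: "To be collected within 72 hours before index procedure and within 72 hours after index procedure". Neither states a number of samples or requires one by 48 hours.
- At discharge, Section 6.4 lists "Lab Measurements (CBC and Platelet count, BUN and Creatinine, and Troponin or CK/CK-MB if patient is discharged prior to 72 hours post-procedure". The sentence could be read as making creatinine conditional on early discharge, but Table 5 marks it at discharge without condition. On timing: "The discharge visit will take place at the time of hospital discharge or at 7 days after the procedure, whichever occurs first".
- Creatinine is drawn again at the 30-day visit.

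**Use.** Section 4.3 lists "Acute kidney injury at 30 days from the index procedure" as a descriptive endpoint. The secondary composite in Section 8.2.5 includes "acute kidney injury (stage 3), or major vascular complications at 30 days". SAP Section 2.3.2 analyses the composite in all attempted subjects, including those who leave before the 30-day visit. SAP Sections 2.3.3 and 2.9 analyse available data, and Protocol Section 8.8 plans no imputation. No rule covers a subject whose post-procedure creatinine values all fall after 48 hours.

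**The concern.** The window in which a creatinine change counts is shorter than the window in which the sample may be drawn. A site can therefore follow the schedule exactly and produce nothing the definition can use. Section 10.10.3 has the Clinical Events Committee adjudicate by the definitions in the protocol, so on the protocol's text a rise first seen at 60 hours fails the creatinine criterion.

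Any error runs in one direction: missed AKI lowers the rate, which favours the device when the results are set beside published rates for approved valves. The loss would also depend on when each site draws blood and how long it keeps patients, which adds between-site variation unrelated to the device.

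The same section shows that tighter timing was feasible. Cardiac biomarkers have three timed draws (about 12-24 h, 36-48 h and 72 h), and footnote 7 of Table 5 ties them to VARC-2. They match the 72-hour peri-procedural infarction window in Appendix II. Creatinine has no corresponding match to its own 48-hour window.

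**Working it through.** The plan gives no figure on this point to reproduce. The check sets the windows side by side and then bounds what can be bounded.

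**1. Windows.** Definition: 0-48 h, reading the clock as starting at the index procedure (an assumption). Section 6.3.1 sampling: 0-72 h. Share of the permitted sampling window outside the definition: (72 − 48)/72 = 24/72 = 33%. This is a share of hours, not of subjects.

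**2. Can a compliant subject have no value inside 48 h?** Three schedules, all compliant:

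| Discharge | Post-procedure creatinine before day 30 | Value inside 0-48 h? |
|---|---|---|
| 40 h | at discharge, 40 h | yes |
| 60 h | 60 h, serving both requirements | no |
| day 4 | 60 h and day 4 | no |

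The discharge sample closes the gap only for subjects discharged and sampled by 48 h. The exposed group is those still in hospital after 48 h whose first post-procedure creatinine is also drawn after 48 h.

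**3. Effect on a rate.** Let R be the true AKI rate, c the part of R that only creatinine would identify (no qualifying urine output, no renal replacement therapy), and f the share of c with no qualifying creatinine by 48 h. If those subjects stay in the denominator as non-events,

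observed rate = R − f × c.

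The documents give none of R (all stages), c or f. At f = 0 nothing is lost. At f = 1/3 (one sample per subject, uniform over 0-72 h, no discharge sample by 48 h) a third of c is lost. At f = 1 all of c is lost.

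**4. Ceiling for stage 3.** Section 1.1.1 cites 30-day stage 2/3 AKI of 1.7%-2.8% for newer valves. Stage 3 alone cannot exceed the combined figure, and c cannot exceed R. If this trial falls in that range, the loss f × c is at most:

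| f (assumed) | at 1.7% | at 2.8% |
|---|---|---|
| 0.10 | 0.17 points | 0.28 points |
| 0.30 | 0.51 points | 0.84 points |
| 1/3 | 0.57 points | 0.93 points |
| 1 | 1.7 points | 2.8 points |

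The true loss is below these values: stage 2 is included in the cited range, dialysed and oliguric patients qualify by other routes, and a subject with another component event is in the composite anyway.

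**5. Baseline.** Two candidates exist: the screening creatinine, which Section 5.2.1 allows from up to 90 days before consent, and the value within 72 h before the procedure. The ratio that defines each stage depends on which is used.

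**The case against.** Much can be said against a stronger version of this point, and most of it stands.

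- A reader might infer that one late sample is all the protocol asks for. It is not: Section 6.3.1 fixes no number, and a discharge creatinine is required as well. Anyone discharged and sampled by 48 h is covered.
- A reader might infer that late-sampled subjects cannot register AKI at all. Urine output qualifies at every stage, and renal replacement therapy is stage 3 regardless. This matters most for the composite, which uses stage 3 only. Table 5 schedules no urine-output measurement, however, so that route relies on recording outside the visit schedule.
- A reader might infer that unassessed subjects are scored as event-free by rule. No passage says so. For the descriptive endpoint, available data could equally mean that they are left out. For the composite, the all-attempted denominator without imputation makes counting them as non-events the natural result, but this is implied, not written.
- The start of the 48 hours is unstated, so part of the problem is ambiguity rather than proven loss. The committee's charter, which is not among the documents, may settle it.
- Sites may draw creatinine together with the early troponin samples, in which case few subjects would be affected.

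These arguments narrow the exposed group and the likely size. They do not supply a creatinine inside the definition window for the subjects in the second and third rows of the table above.

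**Conclusion.** The mismatch is real. Under the protocol as written, a compliant subject who stays beyond 48 h can have no creatinine that the AKI definition accepts. A rise first seen later then counts only if urine output or renal replacement therapy qualifies. The possible bias is downward and falls mainly on the descriptive all-stage AKI rate.

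Its size cannot be derived from the documents. A percentage for the understatement of all-stage AKI would rest entirely on assumed values of f and of the true rate, so none is offered. For the stage 3 component the loss stays below 1 percentage point for f up to 1/3, provided stage 3 AKI here is no more frequent than the cited stage 2/3 range.

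The conclusion assumes that the 48 hours run from the index procedure and that the committee applies Appendix II literally. Nothing confirmatory is at risk: the only hypothesis test is on paravalvular leak in the Portico NG cohort (Section 8.6), and AKI enters neither cohort's success criterion (Section 8.11). This is an inexpensive correction worth making, not a threat to the trial's main conclusions.

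**What to change.** 1. Reconcile Appendix II with Section 6.3.1 and footnote 6 of Table 5, so that definition and sampling share one fixed window. One way is to time the post-procedure creatinine with the blood draws already scheduled at about 12-24 h and 36-48 h. That keeps the named AKIN/VARC-2 definition and adds no venepuncture. Letting the window run to discharge is not a good substitute: discharge sampling extends to day 7, so ascertainment would depend on length of stay.
2. State in Appendix II when the window starts and which pre-procedure creatinine is the baseline.
3. State in the SAP how subjects with no creatinine inside the window are handled for the AKI endpoint and for the composite. Report their number by cohort, instead of silently counting them as free of AKI.

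The cost is a line each in Appendix II, the laboratory schedule and the SAP, with the adjudication charter aligned to match. The reported AKI rate may rise slightly. Subjects sampled under the present schedule cannot be given earlier values, so for them item 3 is the available remedy.
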